#### **8.5 Treatment EEC Session Two / Clinical Trial Exit (Visit 4)**

- Review eligibility criteria ([Section 7.2](#))
- Collect concomitant medications and adverse events ([Sections 7.5 and 9](#))
- Collect vital signs and samples for laboratory testing ([Sections 7.7 and 7.8](#))
- Collect urine sample for pregnancy test ([Section 7.8.3](#))
- Perform VA, SLE, NCT, and dilated fundus exams ([Section 7.10](#))
- Obtain symptom collection (staff-assessed and subject-reported) pre- and post-EEC entry per [Table 2](#) and [Table 4](#) and [Table 3](#) and [Table 5](#) ([Section 7.11](#))
- IP treatment ([Section 7.14](#))
- EEC session ([Section 7.12](#))
- Clinical trial exit

### **9 ADVERSE EVENT REPORTING**

AEs will be collected from the time the subject signs the informed consent form through 30 days after the last IP administration.

#### **9.1.1 Adverse Events**

An AE is any untoward medical occurrence in a patient administered an IP, which does not necessarily have a causal relationship with the IP treatment. Therefore, an AE can be any unfavorable and unintended sign (including an abnormal laboratory finding), symptom, or disease temporally associated with the use of the IP, whether or not it is considered related to the IP.

Abnormal laboratory and other abnormal investigational findings (i.e., physical exam) should not be reported as AEs unless they are associated with clinical signs and symptoms, lead to treatment discontinuation, or are otherwise considered clinically relevant by the investigator. In cases of surgical or diagnostic procedures, the condition/illness leading to such a procedure is considered as the AE rather than the procedure itself. In case of a fatality, the cause of death is considered as the AE, and the death is considered as its outcome.

#### **9.1.1.1 Events Not to Be Considered as Adverse Events**

Pre-existing medical conditions/signs/symptoms present before the EEC Screening Visit (Visit 2) that do not worsen in severity or frequency during the clinical trial are defined as baseline medical conditions, and are not to be considered AEs.

Pregnancies are not considered AEs but must be reported, see [Section 9.1.8](#).

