#### **9.1.1.3 Assessment of Causality and Severity**

For each AE recorded, the investigator will make an assessment of causality and severity as follows:

1. Relationship to IP: The investigator must assess whether they consider an AE to be drug-related. In assessing this relationship, the investigator must use information about the drug as outlined in the Investigator's Brochure, the subject's pre-existent medical conditions/concurrent medication, and chronology of the event relative to drug administration. The following definitions will be used:
  - Definitely Related
  - Probably Related
  - Possibly Related
  - Unlikely to be related
  - Not Related
2. Event Severity: The investigator will be asked to use their medical judgment to assess the severity of the AE.

The following are guidelines to be used by the investigator to judge the event severity of an AE:

3. **Expectedness:** The expectedness of an AE should be determined based on existing safety information about the IP using the following explanations:

- *Unexpected*: an AE that is not listed in the IB or is not listed at the specificity or severity that has been observed.
- *Expected*: an AE that is listed in the IB at the specificity and severity that has been observed.
- *Not applicable*: an AE unrelated to the IP.

AE events that are mentioned in the IB as occurring with a class of products or as anticipated from the pharmacological/mechanical (or other) properties of the product, but are not specifically mentioned as occurring with the particular product under investigation, are to be considered unexpected.

The investigator should initially classify the expectedness of an AE, but the final classification is subject to the determination of the Sponsor's Medical Monitor.

4. Duration: Start and end dates and times, or if continuing.
5. Frequency: whether the event is a single episode, recurrent or continuous.
6. Action taken.
7. Whether it constitutes a SAE, per definition below.
8. Outcome: resolved, resolved with sequelae, continuing, death, or unknown (only for subjects that are lost to follow-up).

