### 9.1.2 Treatment-Emergent Adverse Events

A TEAE is defined as an AE that occurred during the clinical trial after the first dose of IP or was present prior to dosing, and exacerbates after the first dose of IP.

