## **10.8 Safety Analysis**

Adverse events will be coded using the MedDRA dictionary.

Frequencies and percentages will be provided per treatment group of subjects with treatment-emergent adverse events (TEAEs), serious TEAEs, and TEAEs causing premature discontinuation. An adverse event is treatment-emergent if it occurs or worsens after the first dose of randomized study treatment. Furthermore, frequencies will be given of subjects with TEAEs by system organ class, by system organ class and preferred term, by system organ class, preferred term and maximal severity, by system organ class, preferred term and strongest relationship, and by system organ class, preferred term, maximal severity, and strongest relationship. Separate analyses will be performed for ocular specific and all adverse events (including systemic).

Other safety endpoints including visual acuity, slit lamp biomicroscopy, intraocular pressure (IOP), tear osmolarity and dilated fundoscopy will be summarized by treatment group and visit using descriptive statistics. Changes or shifts from baseline will also be summarized where appropriate. For assessments performed by eye, worst eye (study eye) and fellow eye will be summarized separately.

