7.2 Adverse Events

AEs will be coded using the Medical Dictionary for Regulatory Activities (MedDRA) coding dictionary [REDACTED] preferred term (PT) and system organ classification (SOC).

An AE will be considered treatment emergent (TEAE) if it begins or worsens in severity after the first dose of the study drug through 30 days after the last dose of study drug, or the date of initiation of another investigational agent or surgical intervention.

Drug-related TEAEs are defined as definitely related, possibly related, or probably related to study drug. Any AEs with missing relationship to study drug will be considered as related to study drug.

All TEAEs with start dates prior to first dose date in Visit 4 EEC Treatment Session will be classified as AEs occurred in Visit 3 EEC Treatment Session.

An overall summary for number of subjects with events in each treatment will be provided including:

- Number of subjects with at least one TEAE
- Number of subjects with at least one Ocular TEAE
- Number of subjects with at least one drug-related TEAE
- Number of subjects with at least one drug-related Ocular TEAE
- Number of subjects with at least one serious TEAE
- Number of subjects with at least one serious Ocular TEAE
- Number of subjects with at least one TEAE leading to study discontinuation
- Number of subjects with at least one Ocular TEAE leading to study discontinuation

An AE is classified as an ocular AE if system organ class is coded as eye disorders.

The following types of summary for each treatment will be provided. Summaries will be sorted by decreasing frequency of PT within SOC which will be sorted alphabetically.

- TEAEs by SOC and PT
- Ocular TEAEs by SOC and PT
- Non-Ocular TEAEs by SOC and PT
- TEAEs by Casualty, SOC and PT

- Ocular TEAEs by Casualty, SOC and PT
- Non-Ocular TEAEs by Casualty, SOC and PT
- Serious TEAE by SOC and PT
- Ocular Serious TEAE by SOC and PT
- Non-Ocular Serious TEAE by SOC and PT
- TEAE by SOC, PT and maximum Severity
- Ocular TEAE by SOC, PT and maximum Severity
- Non-Ocular TEAE by SOC, PT and maximum Severity
- TEAEs leading to study discontinuation by SOC and PT
- Ocular TEAEs leading to study discontinuation by SOC and PT
- Non-Ocular TEAEs leading to study discontinuation by SOC and PT

If a preferred term or system organ class was reported more than once for a subject, the subject would only be counted once in the incidence for that preferred term or system organ class.

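### SAP 7.2 counts an event already present before dosing as treatment-emergent only if its severity rises, which is narrower than the protocol and leaves out an open event that only becomes more frequent

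*Protocol*

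**What the plan says.** - **Protocol 9.1.1.1** separates AEs from baseline conditions. Conditions present before Visit 2 "that do not worsen in severity or frequency during the clinical trial are defined as baseline medical conditions" and are not AEs.
- **Protocol 9.1.2** includes as a TEAE an event that "was present prior to dosing, and exacerbates after the first dose of IP".
- **Protocol 10.8** states: "An adverse event is treatment-emergent if it occurs or worsens after the first dose of randomized study treatment".
- **Protocol 9** opens with: "AEs will be collected from the time the subject signs the informed consent form through 30 days after the last IP administration". AEs can therefore be on record before the first dose.
- **Protocol 9.1.1.3**, item 5, records for each AE: "Frequency: whether the event is a single episode, recurrent or continuous".
- **Protocol 9.1.1.2** asks for reassessment at each visit. It names changes in severity but not changes in frequency.
- **SAP 7.2** states: "An AE will be considered treatment emergent (TEAE) if it begins or worsens in severity after the first dose of the study drug". Every AE summary it lists counts TEAEs or a subset of them. Its listings include one of all AEs.
- **Protocol 10.3** gives the SAP precedence over the protocol's statistical text.

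**The concern.** The protocol's two TEAE definitions use an unqualified verb for events already present at first dose. The only place where the protocol says what worsening covers names both severity and frequency. The SAP keeps severity alone and gives no reason.

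An event that a product makes more frequent but not more severe could then be missing from the comparison by treatment. It would also be missing from the drug-related counts, even if the investigator judged it related. The omission works in one direction only: it can lower reported TEAE incidence and cannot raise it.

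It also runs against the SAP's other AE conventions, which resolve doubt towards inclusion. Section 4.5 sets incomplete onset dates so that the event counts as treatment-emergent. Section 7.2 counts a missing relationship as related and a missing severity as severe.

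**Working it through.** The plan gives no figure for this point, so the check is a comparison of texts, followed by a count of the tables affected and simple arithmetic.

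**1. What counts as worsening of an event present before first dose**

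| Place | Role | Test |
|---|---|---|
| Protocol 9.1.1.1 | AE or baseline condition | Severity or frequency |
| Protocol 9.1.2 | TEAE | Exacerbation, unqualified |
| Protocol 10.8 | TEAE | Worsening, unqualified |
| SAP 7.2 | TEAE, governs the analysis | Severity only |

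**2. Three cases under SAP 7.2**, each with higher frequency after dosing and unchanged severity

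- (a) An AE recorded between consent and first dose and kept as one open record. It neither begins nor becomes more severe after dosing, so it is not a TEAE.
- (b) A condition present before Visit 2 that becomes an AE only through the higher frequency, with onset recorded as the date of worsening. It begins after dosing, so it is a TEAE and is tabulated.
- (c) As (b), but with the pre-dose onset date recorded. It is not a TEAE.

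Neither document says which onset date to record, so (b) and (c) could be the same event classified in two ways.

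**3. Is there time for case (a)?** The protocol synopsis puts Visit 1 between 2 days and 8 weeks before Visit 2. Protocol 3.1 puts about two weeks between chamber sessions. From Visit 1 to first dose at Visit 3 is therefore about 2 + 14 = 16 days to 8 + 2 = 10 weeks. That interval includes the ragweed session at Visit 2, so an AE still open at first dose is plausible.

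**4. Which outputs are affected?** SAP 7.2 lists 8 overview rows. It also lists 15 tables: five families (SOC and PT; causality; serious; maximum severity; leading to discontinuation), each split into all, ocular and non-ocular. Take a non-serious, drug-related ocular event that does not lead to discontinuation:

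- Overview rows: any TEAE, ocular, drug-related, drug-related ocular = 4 of 8.
- Tables: 3 families (SOC and PT, causality, maximum severity) × 2 (all, ocular) = 6 of 15.

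**5. Effect per subject.** The overview counts subjects with at least one TEAE. With about 126 randomized and all assumed dosed, one omitted subject changes overall incidence by 1/126 = 0.79%, or 0.8 points. The change is zero if that subject has another TEAE. In a single product column the denominator is smaller. Assuming 63 exposed at Visit 3 and 50 at Visit 4 (100 completers split evenly), it is 1/113 = 0.88%, or 0.9 points.

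**The case against.** The strongest defence is that no protocol text says a rise in frequency makes an event a TEAE. Section 9.1.1.1 decides whether a condition is an AE at all, and only for conditions present before Visit 2. The definitions in 9.1.2 and 10.8 never name frequency, and the SAP is entitled to make an unqualified verb operational. This stands as a limit on what 9.1.1.1 proves. It does not remove the point, because the SAP is still narrower than both protocol TEAE definitions.

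A reader might infer more than the documents support:

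- **That any event which only becomes more frequent drops out of every AE table.** The begins limb of SAP 7.2 captures case (b). It also captures a resolved episode that recurs after dosing and is recorded with its own start date. Nor can one event belong to all 15 tables, since it is either ocular or non-ocular.
- **That the event disappears from reporting.** It stays in the listing of all AEs, and SAE reporting under protocol 9.1.5 does not depend on TEAE status.
- **That several subjects, and so several percentage points, are affected.** The documents give no basis for a number. Protocol 4.2 also excludes recent ocular infection or inflammation, blepharitis, dry eye, and chronic ocular conditions likely to worsen, which shrinks the ocular pool.
- **That the comparison between products is biased.** No differential effect has been shown.

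One further objection stands and shapes the fix. The frequency item in 9.1.1.3 classifies the pattern of an event; it does not record a change. Adding a word to the SAP alone could not be programmed reliably.

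**Conclusion.** The mismatch is real and minor. Loss from the TEAE tables is certain only for an AE recorded before first dose, kept as one open record, and more frequent afterwards at unchanged severity. For a pre-existing condition that becomes an AE through frequency alone, loss depends on an onset-date convention that neither document states.

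The ceiling is about 0.8 points of overall TEAE incidence per affected subject. This assumes about 126 dosed subjects and no other TEAE in that subject. The number of such subjects cannot be estimated from the documents and is probably small. The case for acting rests on the one-way direction of the omission, the SAP's own inclusive conventions and the low cost, not on an expected large effect.

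**What to change.** Three changes, which need each other:

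1. In SAP 7.2, define a TEAE as an AE that *begins, or worsens in severity or frequency*, after first dose.
2. In protocol 9.1.1.2, have the reassessment at each visit cover changes in severity or frequency, so that the information exists.
3. State that a worsened pre-existing condition or open AE is recorded with the date of worsening as its onset. SAP 7.2 assigns any TEAE that starts before the first Visit 4 dose to the Visit 3 session. With a pre-dose start date, an event that became more frequent only after the Visit 4 dose would be counted under the Visit 3 product.

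The cost is a few phrases and a small change to the AE recording instructions. TEAE counts may come out slightly higher. The efficacy analysis is not affected.

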#### **9.1.1.2 Recording Adverse Events**

All AEs must be recorded in the site's clinical trial records and the AE electronic CRF. Investigators should use correct medical terminology when recording events and avoid abbreviations.

The investigator should attempt to establish a diagnosis of the AE based on signs, symptoms, and/or other clinical information. The diagnosis, and not the individual signs/symptoms, or laboratory abnormalities, should be documented in the subject's source documents and the CRF unless the etiology of the event is unknown. If signs/symptoms cannot be medically characterized as a single diagnosis or syndrome at the time of reporting, each individual event should be recorded as an AE. If a diagnosis is subsequently established, it should be reported as follow-up information.

An assessment should be made at each visit (or more frequently if necessary) of any changes in severity, the suspected relationship to IP, the interventions required to treat it, and the outcome.

#### **9.1.1.3 Assessment of Causality and Severity**

For each AE recorded, the investigator will make an assessment of causality and severity as follows:

1. Relationship to IP: The investigator must assess whether they consider an AE to be drug-related. In assessing this relationship, the investigator must use information about the drug as outlined in the Investigator's Brochure, the subject's pre-existent medical conditions/concurrent medication, and chronology of the event relative to drug administration. The following definitions will be used:
  - Definitely Related
  - Probably Related
  - Possibly Related
  - Unlikely to be related
  - Not Related
2. Event Severity: The investigator will be asked to use their medical judgment to assess the severity of the AE.

The following are guidelines to be used by the investigator to judge the event severity of an AE:

3. **Expectedness:** The expectedness of an AE should be determined based on existing safety information about the IP using the following explanations:

- *Unexpected*: an AE that is not listed in the IB or is not listed at the specificity or severity that has been observed.
- *Expected*: an AE that is listed in the IB at the specificity and severity that has been observed.
- *Not applicable*: an AE unrelated to the IP.

AE events that are mentioned in the IB as occurring with a class of products or as anticipated from the pharmacological/mechanical (or other) properties of the product, but are not specifically mentioned as occurring with the particular product under investigation, are to be considered unexpected.

The investigator should initially classify the expectedness of an AE, but the final classification is subject to the determination of the Sponsor's Medical Monitor.

4. Duration: Start and end dates and times, or if continuing.
5. Frequency: whether the event is a single episode, recurrent or continuous.
6. Action taken.
7. Whether it constitutes a SAE, per definition below.
8. Outcome: resolved, resolved with sequelae, continuing, death, or unknown (only for subjects that are lost to follow-up).

### 9.1.2 Treatment-Emergent Adverse Events

A TEAE is defined as an AE that occurred during the clinical trial after the first dose of IP or was present prior to dosing, and exacerbates after the first dose of IP.

### 9.1.3 Serious Adverse Events

An SAE is any AE that results in any of the following outcomes:

- death;
- a life-threatening AE;

Note: An AE is considered “life-threatening” if, in the view of either the investigator or Sponsor/designee, the subject is at immediate risk of death as a result of the AE. “Life threatening” does not include an AE that, had it occurred in a more severe form, might have caused death.

- inpatient hospitalization or prolongation of existing hospitalization;

Note: The term “inpatient hospitalization” refers to any inpatient admission (even if less than 24 hours). For chronic or long-term inpatients, inpatient admission includes transfer within the hospital to an acute/intensive care inpatient unit. Inpatient hospitalization does not include: emergency room visits; outpatient/same-day/ambulatory procedures; or admission to observation/short stay units, rehabilitation facilities, hospice facilities, nursing homes, or clinical research/Phase 1 units.

Note: The term “prolongation of existing hospitalization” refers to any extension of an inpatient hospitalization beyond the stay anticipated or required for the reason for the initial admission, as determined by the investigator or treating physician.

- a persistent or significant incapacity or substantial disruption of the ability to conduct normal life functions;

Note: A serious adverse event (SAE) specifically related to visual threat would be interpreted as any potential impairment or damage to the subject’s eyes (e.g., hemorrhage, retinal detachment, central corneal ulcer, or damage to the optic nerve).

- a congenital anomaly/birth defect; and,
- other serious (Important Medical Events) events that do not fit other outcomes, where the event may jeopardize the subject and may require medical or surgical intervention to prevent one of the outcomes listed in the SAE definition, based upon appropriate medical judgement.

#### **9.1.4 Unexpected Adverse Events**

An unexpected adverse event is defined as an AE, the nature or severity of which is not consistent with the information in the Investigator’s Brochure.

#### **9.1.5 Reporting Serious Adverse Events**

The investigator is responsible for reporting all SAEs, regardless of causality, to the Sponsor designee within 24 hours of learning of the occurrence. SAEs should be sent to: [REDACTED]  
[REDACTED]

(Local toll-free numbers will be provided on the SAE report form cover sheet.)

The reporting timeframe starts when the subject signs the informed consent or assent form through 30 days after the last IP administration. At a minimum, a description of the event and the Investigator’s judgment of causality must be provided at the time of the initial report. These preliminary reports will be followed by detailed descriptions that will include copies of hospital case reports, autopsy reports, and other documents when requested and applicable.

A follow-up SAE Report must be submitted within 24 hours of the investigator receiving the follow-up information (such as information regarding complications, progression or resolution).

An SAE that is considered completely unrelated to a previously reported event should be reported separately as a new SAE.

The procedures for reporting SAEs are as follows:

- Complete the “Serious Adverse Event Report Form.” The investigator may contact Pharmacovigilance via the telephone hotline for assistance with SAE reporting.
- Fax or email the SAE Form to the attention of Pharmacovigilance within 24 hours of the investigator’s knowledge of the event.

The original copy of the SAE Report Form and the fax confirmation sheet (or email) must be kept with the source documentation at the clinical trial site.

Follow-up information should be communicated the same way, using a new SAE Report Form stating that it is a follow-up to the previously reported SAE and giving the date of the original report. The follow-up information should describe whether the event has resolved or continues, if and how it was treated, and whether the subject continued or withdrew from clinical trial participation.

The investigator and qualified site staff should institute any supplemental investigations of SAEs based on their clinical judgment of likely causative factors. This may include clinical laboratory tests not specified in the protocol, histopathologic examinations, or consultations with specialists. The Sponsor or their designee may also request the investigator to conduct supplemental assessments.

If the SAE was not previously documented in the Investigator’s Brochure and is thought to be related to IP, the Sponsor or their designee may urgently require further information from the investigator for regulatory authority reporting. The Sponsor may need to issue an investigator Notification to inform all investigators involved in any clinical trial with the same drug that this SAE has been reported.

The investigator should notify Pharmacovigilance of any death or SAE occurring after a subject has withdrawn from the clinical trial when such a death occurs within 30 days of the last dose of IP and may reasonably be related to the IP.

